#### 4.13.2 CL/F and Body Size

Relationships between CL/F and body size (body weight [kg] and BMI [ $kg/m^2$ ]) will be evaluated graphically for the Japanese and non-Japanese cohorts and with combined cohort data. If suggested by the graphs, regression models may be fit to the data

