Abbreviations:  $AUC_{\infty}$  = area under the plasma concentration versus time curve with the last concentration extrapolated based on the  $\lambda_z$ ;  $AUC_{(0-t)}$  = area under the plasma concentration versus time curve to the last measurable concentration; CL/F = clearance/bioavailability;  $C_{max}$  = maximum observed concentration; EC = enteric-coated;  $\lambda_z$  = elimination rate constant; PPI = proton pump inhibitor;  $t_{1/2}$  = terminal elimination half-life;  $T_{lag}$  = lag time;  $t_{max}$  = time to maximum concentration; UC = uncoated capsule; Vz/F = apparent volume of distribution.

A total of 18 subjects were enrolled, completed the study, and were included in the safety analysis. There were no deaths, SAEs, or discontinuation due to AEs in this study. Overall, a total of 21 AEs were reported by 7 (39%) subjects in this study. The percentages of subjects reporting AEs following ALXN1840 dosing were similar following each of the 3 study treatments. All AEs reported in the study were mild (Grade 1) in severity. Diarrhea, headache, and nasal congestion were the most frequently reported AEs in this study and were each reported by 2 (11%) subjects. There was 1 AE considered by the Investigator to be probably related to study drug (nausea) and 5 AEs considered to be possibly related to study drug (4 events of diarrhea and 1 event of nausea); all other AEs were considered to be unrelated to the study drugs. There were no clinically important trends in the laboratory, vital sign, ECG, or physical examination assessments in this study.

There were no apparent relationships between clearance/bioavailability (CL/F) and body size (weight, body mass index [BMI]) in either Study WTX101-101 or Study WTX101-102,

b Parameter could not be estimated for any subject for this treatment.

suggesting that a fixed dose, rather than a dose based on body size (ie, mg/kg or mg/m²) may be appropriate for ALXN1840.

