### Weight

2. Body weight  $\leq 80 \text{ kg}$  and BMI within the range  $18 - 25 \text{ kg/m}^2$ , inclusive, at screening.

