**Figure 1: Study WTX101-HV-106 Schematic**

### 3.3 Sample Size

The study sample size is not based on hypothesis testing with statistical considerations. A sample size of 20 subjects (10 subjects in each cohort) has been selected based on practicality and convention for this type of study. Considering potential for subject drop-out of the study, a total of 24 subjects will be enrolled with 12 Japanese and 12 non-Japanese. The between-subject coefficient of variation (CV) in a previous bioavailability study using  $2 \times 30$  mg EC tablets (Study WTX101-102) was 35%, which can be used to approximate the standard deviation (SD). Two cohorts of 10 subjects produce a two-sided 90% confidence interval with a distance from the difference in means to the limits that is equal to 0.271. For example, if the difference of means is zero and the ratio of means is 1, this level of precision corresponds to an interval from 0.76 to 1.31 on the ratio scale.

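### CL/F is regressed on body size only if the plots suggest it, so a flat-looking plot leaves no slope or confidence limit and may be read as no relationship

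*SAP*

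**What the plan says.** SAP 4.13.2 states that the relation of CL/F to body weight and BMI "will be evaluated graphically for the Japanese and non-Japanese cohorts and with combined cohort data". It then adds: "If suggested by the graphs, regression models may be fit to the data". Protocol 9.4.3.1.3 carries the same sentence and defers detail to a PK/PD data analysis plan. The SAP repeats the sentence without adding a criterion, a model, a scale, an interval or a rule for reading an unremarkable plot.

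The neighbouring exploratory analysis, dose proportionality in SAP 4.13.1, is given a power model with 90% and 95% confidence intervals. The cohort comparison in SAP 4.12.3 has cohort, period and subject in the model and no body-size term.

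Protocol 2.2 shows how such plots have been used before. On two earlier studies of 18 subjects each it reports "There were no apparent relationships between clearance/bioavailability (CL/F) and body size (weight, body mass index [BMI" (cut here at the bracket) and continues "suggesting that a fixed dose, rather than a dose based on body size", may be appropriate.

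**The concern.** The decision to estimate depends on the look of the data, and it can go wrong in both directions.

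- **Flat-looking plot.** No slope and no confidence limit are produced. Nothing separates a relationship that is absent from one that 20 to 24 subjects could not show. Inclusion criterion 2 (weight at most 80 kg, BMI 18 to 25) narrows the weight range, which makes a flat appearance more likely.
- **Sloped-looking plot.** A slope fitted only in trials that happen to look sloped overstates the true slope on average.

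Weight and BMI are the only covariates that the plan relates to clearance. In a Japanese versus non-Japanese comparison, whether an exposure difference follows body size is a natural next question. Protocol 2.2 already ties the answer to whether dosing needs to depend on body size.

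A smaller issue is that the cohorts may differ in weight. If a regression on the combined data left cohort out, a cohort difference in CL/F could then appear as a weight slope.

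**Working it through.** **The plan's own precision figure.** SAP 3.3 gives a 90% half-width of 0.271 for the cohort difference with 10 per cohort. Check: t(0.95, 18 df) × 0.35 × √(2/10) = 1.734 × 0.35 × 0.447 = 0.271, and exp(±0.271) = 0.76 to 1.31. It reproduces. No such figure is given for the body-size analysis.

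**Inputs from the documents**
- Subjects: 20 completers, 24 enrolled (SAP 3.3).
- Between-subject CV 35%, used directly as SD 0.35 (SAP 3.3). The exact log SD is √ln(1 + 0.35²) = 0.34.
- CL/F for the fasted EC tablet, 0.92 ± 0.51 (Protocol Table 4): CV = 0.51/0.92 = 55%, log SD = √ln(1 + 0.554²) = 0.52.
- AUC∞ in the same column, 17,258 ± 5,955: CV 34.5%. CL/F is dose divided by AUC∞, so under a lognormal the two CVs would agree. They do not, hence the range 0.35 to 0.52.

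**Assumptions, because the documents give no value**
- Weight mean 62 kg, SD 7 to 11 kg, truncated to 44–80 kg.
- True exponent 1 (CL/F proportional to weight), with 0.75 as a sensitivity case.
- A two-sided 5% test of the slope stands in for visual judgement.
- One CL/F value per subject. Two doses per subject could add some power, but no within-subject CV is given.

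**Missed effects.** Simulated log CL/F = b × log(weight/62) + normal error, 20,000 trials per cell. Share of trials with slope p ≥ 0.05 when b = 1, shown as n=20 / n=24:

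| Weight SD | SD of ln weight | log SD 0.35 | log SD 0.46 | log SD 0.52 |
|---|---|---|---|---|
| 7 kg | 0.11 | 75% / 70% | 84% / 80% | 86% / 84% |
| 9 kg | 0.13 | 68% / 60% | 79% / 75% | 82% / 79% |
| 11 kg | 0.14 | 62% / 54% | 76% / 71% | 80% / 76% |

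For b = 0.75 and log SD 0.35 to 0.46, the share is about 71% to 89%.

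A separate noncentral-t calculation agrees. At SD of ln weight 0.14 and log SD 0.34, power is 39% / 46%, so 61% / 54% are missed.

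**Where the share falls below half**
- If 0.35 is the total SD rather than the residual SD after weight, the 11 kg, n=24 cell drops to about 48%.
- If weights were spread evenly over about 45–80 kg (SD of ln weight 0.166), log SD 0.34 gives 49% / 41%, or 38% / 30% if that SD is also taken as total.

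**Interval width.** Half-width = t(0.975, n−2) × SD / (SD of ln weight × √(n−1)).
- Narrow end, n=24: 2.074 × 0.35 / (0.142 × 4.796) = 1.07.
- Wide end, n=20: 2.101 × 0.52 / (0.110 × 4.359) = 2.28.

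An estimate near 0 would not exclude 1 anywhere in this grid. With SD of ln weight 0.166 and log SD 0.34, the half-width is 0.99 / 0.89, and it just would.

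**Selection.** With n=24, b = 1 and log SD 0.35 to 0.46, slopes that reach significance average 1.4 to 2.2.

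**Combined data without a cohort term.** 12 + 12 subjects, no true weight effect, within-cohort weight SD 8 kg, log SD 0.35 to 0.46, cohort ratio of CL/F 1.25 to 1.5:

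| Weight gap | False slopes significant at 5% | With a cohort term |
|---|---|---|
| 5 kg | 6% to 10% | about 5% |
| 10 kg | 9% to 23% | about 5% |

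**The case against.** Several points on the other side have force.

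- **No reading rule is set.** A reader might infer that a flat plot will be reported as no relationship. Neither SAP 4.13.2 nor Protocol 9.4.3.1.3 says so, and a purely descriptive report is equally open. The support is the Protocol 2.2 precedent, which is itself hedged. This objection stands: the documents bear out a risk, not a stated rule.
- **The miss rate rests on assumptions.** A reader might infer that the plot would miss a full weight effect in most trials, without qualification. Weight spread, effect size and the 5% stand-in are all assumed, and the share falls below half at the favourable end. This stands, and the figure must be given as a conditional range.
- **Confounding is partly covered.** A reader might infer that the combined analysis is confounded by cohort. Separate cohort plots are planned, nothing says a regression would omit cohort, and both cohorts share the same weight and BMI limits. What remains is that no model is written down. At a 5 kg gap the distortion is small.
- **Detail may sit elsewhere.** The protocol defers to a data analysis plan. SAP 4.12 bears a similar title, but body size falls under 4.13, where the conditional sentence is repeated unchanged. A separate document specifying slope and interval would meet the point. None is among the documents.
- **Little depends on it.** Body size is not a listed objective or endpoint. CL/F, weight and BMI are all listed by subject, so a slope could be computed later. This limits the severity, but a slope computed afterwards is not prespecified.
- **Always fitting adds no power.** True. The gain is a stated limit in place of an unbounded visual verdict.

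**Conclusion.** The point holds as a prespecification weakness in an exploratory analysis. The conditional rule gives no estimate when the plot looks flat and an upward-selected one when it does not.

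Under the stated assumptions, a proportional weight effect would escape notice in roughly 50% to 85% of trials of 20 to 24 subjects. The exponent would be known only to within about ±1.1 to ±2.3. Both figures improve when weights are spread more widely and the CV is at the 35% used for sizing; the share missed then falls below half. They worsen if the CL/F row of Table 4 is the better guide.

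The documents do not support saying that a flat plot will be declared evidence of no relationship, only that it may be, as in Protocol 2.2. The cohort-confounding element is conditional on a model that leaves cohort out. The primary geometric mean ratio is unaffected. The change is desirable rather than essential.

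**What to change.** Replace the conditional sentence in SAP 4.13.2 with:

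> Regardless of the appearance of the graphs, log(CL/F) will be regressed on log(body weight), and separately on log(BMI), with cohort and dose as fixed effects and subject as a random effect. The slope will be reported with its 95% CI, and absence of a relationship will not be concluded from the graphs or from a CI that includes zero.

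This matches the level of detail already given to dose proportionality in SAP 4.13.1. Protocol 9.4.3.1.3 leaves detail to the analysis plan, so the SAP can carry the wording.

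The cost is a short SAP edit and one small table from data already collected. The interval will be wide, so a statement that body size does not matter will be harder to support.

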#### 4.13.3 Pharmacodynamic and Biomarker Analyses

Individual ALXN1840 PD and biomarkers, assessed as plasma total Cu (PD), NCC (PD),  $NCC_{corrected}$  (PD), Cp (biomarker), and CpC (biomarker) concentration-time data (including measured, absolute and percent changes from baseline) will be listed and summarized at each time point by cohort and period with descriptive statistics. The NCC level will be corrected for the amount of Cu bound to the TPC ( $NCC_{corrected}$ ).

Individual subject data (and change from baseline) of plasma Cp and copper levels (total Cu, Cp, CpC and NCC) will be presented graphically for each cohort and period. Mean plots (for measured and change from baseline value) of cohort and dose will be overlaid (separately for PD and biomarker parameters) and presented over time.

Analyses of other biomarker data including, but not limited to, those of PUF Cu may be conducted.

### 4.14 Methods for Withdrawals, Missing Data and Outliers

The individual plasma concentration data and the actual timing of study drug administration and blood sampling will be used throughout the analyses. If there is any doubt about the actual time at which a sample was taken, then the scheduled time will be used. For PK data analysis, please see Section 4.12.1 regarding the handling of missing and BLQ values. For PD data analysis, there will be no imputation for missing values.

AEs with unknown start date/time will be assumed to be treatment-emergent unless the end date/time is known to be before the first administration of study drug. Otherwise missing or partial dates will be listed as such.

There will be no further imputation of missing data (i.e., subjects who prematurely discontinue from the study will not be included in summary statistics or analyses beyond the time of discontinuation).

Depending on the extent of missing values, the appropriateness of the methods described for handling missing data may be reassessed prior to database lock (to examine the sensitivity of results to handling of missing data).

